#### 7.7.2 LABORATORY TESTS

Laboratory tests (hematology, clinical chemistry, coagulation, urinalysis, and thyroid functions) will be performed at the timepoints specified in Appendix C, which also contains a complete list of all clinical laboratory tests. Clinical laboratory evaluations and CFB for each laboratory value will be listed and summarized using descriptive statistics by treatment and visit for visits with at least 4 subjects in either treatment group for the Safety Population. If a laboratory test is repeated during a visit, only the first values will be included in the summary; all values will be included in the listings. Clinically significant (CS) out-of-range laboratory values should be recorded as AEs. ALT (Alanine Aminotransferase; SGPT) and AST (Aspartate Aminotransferase; SGOT) are referred to as ALAT (SGPT) and ASAT (SGOT), respectively, in the listing of Blood Chemistry parameters. Urinalysis laboratory values will be listed only and CFB will not be computed. Laboratory assessments that are considered exploratory efficacy variables (Section 7.6.7) will be presented both as efficacy variables and laboratory variables, through Cycle 11 when considered exploratory efficacy variables and for all visits when considered safety variables.

#### 7.7.3 ECOG PERFORMANCE STATUS

ECOG Performance Status (PS) is an assessment using a five-point scale, with 0= Normal activity,..., 5=100 % bedridden; details are given in Appendix D. ECOG PS will be recorded at Pre-study visit, Day 1 of Cycle 1 (Baseline), Day 1 of each subsequent cycle, and at Follow-up. ECOG PS and categories of CFB in ECOG PS (decreased, no change, increased) will be presented for the Safety Population by treatment and cycle for cycles with at least 4 subjects in either treatment group.

#### 7.7.4 VITAL SIGNS AND WEIGHT

Vital signs will be recorded at Days 1 and 15 of each cycle, Day 8 of Cycle 1, Hours 1, 2, 3, 4, 6 and 8 on Cycle 1 Day 1, and at Follow-up. Systolic blood pressure (mmHg), diastolic blood pressure (mmHg), respiratory rate (breaths/min), pulse (beats/min), oral temperature (degrees C), and CFB for each of these vital signs will be listed and summarized using descriptive statistics for the Safety Population by treatment and visit for visits with at least 4 subjects in either treatment group. Height (cm) will be recorded at the Pre-Study Visit only and will be included in listings only. Body weight (kg) will be recorded at Days 1 and 15 of each cycle, Day 8 of Cycle 1, and at Follow-up; BMI (kg/m²) will be computed for each of these visits using the height recorded at the Pre-Study Visit.

#### 7.7.5 ECG PARAMETERS

A resting 12-lead electrocardiogram (ECG) will be performed at the Pre-Study visit, Days 1 and 15 of all cycles, Day 8 of Cycle 1, and at 2, 4, and 6 hours post-dose on Day 1 of Cycle 1, and at Follow-up. ECG interval data (Heart Rate [HR], PR, QRS, QT) and the corresponding CFBs will be listed and summarized using descriptive statistics for the Safety Population by treatment and visit for visits with at least 4 subjects in either group. OTc will be computed using Fridericia's treatment QTcF=QT\*(HR/60)1/3. QT will not be summarized and will be included in the listing only. ST Segment (normal or abnormal), Cardiac Rhythm (normal or abnormal), and Overall Impression (normal, abnormal- NCS, or abnormal- CS) will be summarized using counts and percentages for the Safety Population by treatment and visit.

#### 7.7.6 PHYSICAL EXAMINATIONS

A physical examination (PE) will be performed at every visit. A complete PE will be performed at the Pre-Study, Cycle 1 Day 1 (the Baseline Visit if the Pre-Study visit not performed within 3 days prior), and End of Study/End of Dosing (EOS) visits, including a thorough review of all body systems (general appearance, head/neck, ears/nose/throat, skin, chest/lungs, heart, abdomen, genitourinary, extremities, musculoskeletal, lymph nodes, neurological and other, specify) as well as measurement of weight (kg) and height (cm). At all other visits, a symptom-directed PE, including weight (kg), will be performed. If the Pre-Study visit is within 3 days of Cycle 1 Day 1, then no responses should be reported for Cycle 1 Day 1.

At the Pre-Study visit, each body system, including "Other" (specify) if appropriate, will be assessed (Normal, Abnormal, or Not Done). At each visit after the Pre-Study visit, assessments will be recorded for any body systems with clinically significant (CS) changes from the PE conducted at the previous assessment (Normal, Abnormal, or Not Done), with details. The CRF indicates that these assessments should be recorded if the body system with a clinically significant change from the PE conducted at the previous assessment is "Abnormal", with a description of the abnormality; these assessments should be recorded for any CS change from the previous PE, not just "Abnormal", including a CS change from "Abnormal" to "Normal".

Assessments at the Pre-Study visit will be summarized by body system (Normal or Abnormal). Any subject with more than one assessment of "Other" will be counted once. Assessments recorded as "Not Done" will not be included in the table. Any description of an abnormality will be included in the corresponding listing. At each visit after the Pre-Study visit, the number of subjects with at least one CS change from the PE conducted at the previous assessment will be summarized for the Safety Population by treatment and visit for visits with at least 4 subjects in either treatment group. Any body systems with a CS change from the PE conducted at the previous assessment will be included in the corresponding listing with the result and description.

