Safety data analysis will be conducted on all subjects receiving at least 1 dose of CF102 or matching placebo. The number and percentage of subjects experiencing 1 or more AEs will be summarized by treatment group, relationship to study drug, and severity. AEs will be coded using Medical Dictionary for Regulatory Activities (MedDRA™) terminology. Listings of subjects who experienced dosing interruptions and dose reductions, withdrawal due to an AE, serious AEs and/or death will be presented. Laboratory parameters, other than Liver Chemistry Tests (see below), INR, and viral load, will be summarized using descriptive statistics and data listings of clinically significant abnormalities. Liver Chemistry Tests, INR, and viral load will be presented as exploratory efficacy variables. Vital signs, ECOG PS, physical examination, and ECG data will be summarized by changes from baseline values for each treatment group using descriptive statistics.

Exploratory Analyses:

Certain laboratory parameters associated with hepatic dysfunction and cirrhosis will be examined. These include: Chemistry (bilirubin [direct and total], ALT, AST, and albumin, referred to collectively as “Liver Chemistry Tests”); INR; and viral load. These parameters will be summarized using descriptive statistics and clinically significant abnormalities will be listed. Additionally, between-treatment comparisons will be performed using ANCOVA with the baseline value used as a covariate. The relationship between WBC A₃AR expression and clinical response will be assessed by providing the counts and percentages for Overall Response by Change from Baseline (CFB) in A₃AR expression categorized as less than or at least the median by treatment at each visit.

Table 1–1: Schedule of Events for Double Blind Portion of the Trial

Trial Procedures	Pre-Study (-28 Days)	Cycle 1		Subsequent Cycle		End of Study/End of Dosing (EOS) ¹	Follow-up (28 ± 3 Days Post EOS)
		Day 1 Baseline	Days 8 and 15 ±2 Days	Day 1 ±2 Days	Day 15 ±2 Days	Day 1 ± 2 Days	
Medical and disease history	X						
Physical examination	X ^a	X ^{a,c}	X ^b	X ^b	X ^b	X ^a	X ^b
Inclusion/exclusion criteria	X	X					
Informed consent	X						
Body weight	X	X ^c		X		X	X
Vital signs ^d	X	X	X	X	X	X	X
Clinical laboratory testing ^e	X	X ^c	X	X	X	X	X
T3, T4, TSH	X	X		X		X	X
ECG ^f	X	X	X ^f	X	X	X	X
Pregnancy test (serum) ^g	X	X ^c		X		X	X
ECOG PS ^g	X	X ^c		X		X	
α-fetoprotein (AFP)		X		X		X	X
WBC A ₃ AR sample		X		X ^h			
PK samples		X ^k	X ^k	X ^k			

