4.5 Potential Risks and Benefits of Therapy

4.5.1 Risks

Adverse events observed during CF102 therapy in the CF102-102HCC trial included the following:

- Most common AEs (4 or more occurrences, all causalities combined): abdominal pain, ascites, diarrhea, edema, fatigue, fever, lack of appetite, pain, and weakness.
- AEs considered possibly or probably related to CF102: pain in various bodily locations, fatigue, diarrhea, lack of appetite, weakness, and fever.
- Of the 25 serious adverse events reported, ascites, cellulitis, cerebral hemorrhage, headache, hyponatremia, and leg thrombus were considered at least possibly related to CF102.

For additional information, please refer to the Investigator Brochure.

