12.4.3 Safety Data

Safety observations and measurements including study drug exposure, adverse events, laboratory data, physical examination findings, vital signs, ECG, and ECOG PS will be summarized and presented in tables and listings.

Laboratory parameters including thyroid functions will be summarized using descriptive statistics and data listings of clinically significant abnormalities. Physical examinations, vital signs, ECOG PS, and ECG data will be summarized by changes from baseline values for each treatment using descriptive statistics. Liver Chemistry Tests, INR, and viral load will be presented as exploratory efficacy variables.

Adverse events will be coded using the MedDRA™ dictionary. The number and percentages of subjects experiencing AEs will be tabulated by system organ class and preferred term. Assessments of AEs will include characterization of the type, incidence, severity, seriousness, and relationship to treatment. Summary subject listings will be provided for subjects with dose interruptions and dose reductions, SAEs, AEs resulting in discontinuation from the trial, and deaths. Adverse events will be graded according to NCI-CTCAE criteria, version 4.0.

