Includes visits with at least 4 subjects in either treatment group

Source: Listing 16.2.10.2.

Programming Notes: Continue for ST Segment and Cardiac Rhythm (Normal, Abnormal, and Total) and all visits (Pre-Study visit, Days 1 and 15 of all cycles, Day 8 of Cycle 1, and at 2, 4, and 6 hours post-dose on Day 1 of Cycle 1, and at Follow-up). Include visits with at least 4 subjects in either treatment group.

Table 14.3.10.1 Physical Examination at Pre-Study Visit Safety Population

		CF102	Placebo
Body System	Response, n (%)	(N=xx)	(N=xx)
General Appearance	Normal	xxx (xx.x)	XXX (XX.X)
	Abnormal	xxx (xx.x)	xxx (xx.x)
	Total	xxx	XXX
Head and Neck	Normal	xxx (xx.x)	xxx (xx.x)
	Abnormal	xxx (xx.x)	xxx (xx.x)
	Total	xxx	XXX
Eyes, Ears, Nose, Throat	Normal	xxx (xx.x)	xxx (xx.x)
	Abnormal	xxx (xx.x)	xxx (xx.x)
	Total	XXX	XXX
Skin	Normal	xxx (xx.x)	xxx (xx.x)
	Abnormal	xxx (xx.x)	xxx (xx.x)
	Total	xxx	XXX
Chest / Lungs / Breast	Normal	xxx (xx.x)	xxx (xx.x)
	Abnormal	xxx (xx.x)	xxx (xx.x)
	Total	xxx	XXX
Heart	Normal	xxx (xx.x)	xxx (xx.x)
	Abnormal	xxx (xx.x)	xxx (xx.x)
	Total	XXX	xxx
Neurological	Normal	xxx (xx.x)	xxx (xx.x)
	Abnormal	xxx (xx.x)	xxx (xx.x)
	Total	XXX	XXX
Other (1)	Normal	xxx (xx.x)	xxx (xx.x)
(-,	Abnormal	xxx (xx.x)	xxx (xx.x)
	Total	XXX	XXX

(1) Subjects with more than one assessment of "Other" are counted once. Percentages are calculated using the number of subjects in the Safety Population for each treatment as the denominator.

Abnormalities are provided in the listing.

Source: Listing 16.2.11 .1

Programming Notes: Include other body systems. Subjects with more than one assessment of "Other" are counted once. Do not include "Not Assessed".

Table 14.3.10.2 Physical Examination Safety Population

Visit	Clin. Sig.	CF102	Placebo
	Changes (1), n (%)	(N=xx)	(N=xx)
Cycle 1 Day 1	Yes	XXX (XX.X)	XXX (XX.X)
	No	xxx (xx.x)	xxx (xx.x)
	Total	XXX	XXX
Cycle 1 Day 8	Yes	xxx (xx.x)	xxx (xx.x)
	No	xxx (xx.x)	xxx (xx.x)
	Total	XXX	XXX
Cycle 1 Day 15	Yes	xxx (xx.x)	xxx (xx.x)
	No	xxx (xx.x)	xxx (xx.x)
	Total	XXX	XXX
Cycle 2 Day 1	Yes	xxx (xx.x)	XXX (XX.X)
	No	xxx (xx.x)	xxx (xx.x)
	Total	XXX	XXX
Cycle 2 Day 15	Yes	xxx (xx.x)	xxx (xx.x)
	No	xxx (xx.x)	xxx (xx.x)
	Total	xxx	XXX

 Are there any clinically significant changes from the physical examination conducted at the previous assessment?

Source: Listing 16.2.11.2

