		Cycle 4 Day 1		No			
xxx/xxxxx	xxxxx	Cycle 1 Day 1	Yes				
		Cycle 1 Day 8		No			
		Cycle 1 Day 15		No			
		Cycle 2 Day 1		Yes			

 Are there any clinically significant changes from the physical examination conducted at the previous assessment? Baseline=Cycle 1 Day 1

Programming Notes: Continue for other cycles. If there are 'No' clinically significant changes from the physical examination conducted at the previous assessment, then the assessments for individual body systems should not be completed.

If "Clin, Sig, Changes" = 'Yes', then results should be recorded for at least one body systems with a "Result" differing from the previous assessment list. If "Screening <= 3 days from Baseline?" is Yes, there should be no responses for Cycle 1 Day 1.

Listing 16.2.12 **Prior and Concomitant Medications** 

Site/ Subject	Treatment	Medication	ATC Level 3	Reason for Use	AE no. (1)	Dose & Units	Regimen	Route (2)	Start Date Stop Date (3)
xxx/xxxxx	XXXXX	XXXX	XXXX	XXXXX	Х	XXXX	XXXX	XX	DD/MM/YY
xxx/xxxxx	xxxxx	XXXX	xxxx	xxxxx	x	xxxx	xxxx	xx	DD/MM/YY DD/MM/YY DD/MM/YY
xxx/xxxxx	xxxxx	xxxx	xxxx	XXXXX	х	xxxx	xxxx	xx	DD/MM/YY O

Includes medications taken within 30 days prior to Screening Visit.

Programming Note: Sort by start date for each subject.

 Blank if Not Applicable
(2) 1=PO; 2=IV; 3=SC; 5=IM; 11=T; 12=OU,OS,OD; 13=AU,AS,AD; 14=IN; 15=PV; 16=PR; 24=SL; 30=BUC; 37=IA; 71=NG; 136=INH; 358=TD; 135=Other; 139= Unknown

 O=Ongoing

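### The post-baseline physical-examination table counts any significant change since the last exam, in either direction, although the protocol specifies change from baseline, so its Yes counts cannot be read as harm

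*SAP*

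**What the plan says.** Protocol 12.4.3 states: "Physical examinations, vital signs, ECOG PS, and ECG data will be summarized by changes from baseline values for each treatment using descriptive statistics". The Synopsis says the same: "Vital signs, ECOG PS, physical examination, and ECG data will be summarized by changes from baseline values for each treatment group".

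SAP 7.7.6 sets a different rule for visits after Pre-Study: "the number of subjects with at least one CS change from the PE conducted at the previous assessment will be summarized". On direction, it notes that the CRF asked for body-system entries when the changed system was Abnormal, and then says "these assessments should be recorded for any CS change from the previous PE, not just" Abnormal ones. It names a change from Abnormal to Normal as included.

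Shell Table 14.3.10.2 has Yes, No and Total rows at each visit, and its footnote defines the question: "Are there any clinically significant changes from the physical examination conducted at the previous assessment". Percentages use the whole Safety Population of each arm. Body system, result and description go only to Listing 16.2.11.2. The programming note there says that, where the answer is No, "then the assessments for individual body systems should not be completed".

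SAP Section 9 lists differences from the protocol, including the rule that by-visit safety summaries need at least 4 subjects in either arm. It does not list the changed reference point for PE. Its closing sentence leaves undeclared changes to the clinical study report.

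**The concern.** A between-arm safety table should let the reader see which arm did worse. Here, two features of the rule prevent that. The reference is the previous examination, so a lasting change is visible only at the visit where it appears. Direction is also pooled, so an arm with more Yes answers may have had more new findings or more recoveries.

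The abdomen and extremities are among the systems examined, and Protocol 4.5.1 reports that in the earlier HCC trial "ascites, cellulitis, cerebral hemorrhage, headache, hyponatremia, and leg thrombus were considered at least possibly related to CF102". Ascites is a finding that a physical examination can show, so the table ought to be interpretable for it.

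PE is also the exception among the four assessments that the protocol names together. SAP 7.7.4 and 7.7.5 give change from baseline for vital signs and ECG intervals. SAP 7.7.3 gives change from baseline in ECOG PS as decreased, unchanged or increased. The SAP therefore already has a baseline-referenced display, split by direction, for an ordinal assessment.

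**Working it through.** No power or error-rate figure bears on this point. The check sets the rules side by side and applies them to hypothetical subjects.

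**Inputs**
- Protocol 12.4.3 and Synopsis: the reference is baseline.
- SAP 7.7.6: the reference is the previous PE, and either direction counts.
- SAP 7.7.6: "A physical examination (PE) will be performed at every visit", so the previous PE is normally the one at the previous visit.
- Listing 16.2.11.2 note: no body-system result is entered when the answer is No.

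**Applying the SAP rule** to one body system, with no other change, at Cycle 1 Day 8, Cycle 1 Day 15, Cycle 2 Day 1, Cycle 2 Day 15 and Cycle 3 Day 1:

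| Subject | Status at baseline, then over the five visits | SAP table | Against baseline |
|---|---|---|---|
| (a) | Normal; Abnormal at all five | Yes, No, No, No, No | worse at 5 of 5 |
| (b) | Normal; Abnormal at the first, Normal afterwards | Yes, Yes, No, No, No | worse at 1 of 5 |
| (c) | Abnormal; Normal at all five | Yes, No, No, No, No | better at 5 of 5 |

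Subjects (a) and (c) have opposite courses and identical table entries. Subject (b) has more Yes answers than (a), although (b) recovered and (a) did not. The second Yes for (b) is the recovery itself.

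At the first post-baseline visit the previous PE is the baseline PE, so the reference points coincide there, but direction is still pooled. Subject (a) returns to No only if no other body system changes significantly at the later visits.

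**Denominator.** Planned enrolment is 78 with 2:1 allocation, so the CF102 arm would have about 78 × 2/3 = 52 subjects. If all of them enter the Safety Population and a late visit has 4 CF102 subjects examined (enough to be displayed), all answering Yes, the shell prints 4/52 = 7.7%. Among those examined it is 4/4 = 100%. Percentages therefore shrink as subjects leave, whatever is found.

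**The case against.** The strongest reply is that little depends on this table. New ascites is an unfavourable sign and so is reportable as an adverse event. SAP 7.7.1 counts events that start on treatment, or are present at baseline and increase in severity, as treatment-emergent, and Tables 14.3.1 to 14.3.3 tabulate them. Listing 16.2.7 gives start and stop dates and outcome, serious events have their own listing, and weight is summarised by change from baseline in Table 14.3.8. Direction can be recovered per subject from Listing 16.2.11.2. All of this stands, and it limits the point to the tabulation of PE-form results.

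A reader might go further in four ways that the documents do not support:
- That post-baseline physical findings are summarised nowhere else. The adverse event tables contradict this.
- That arms with very different end states would print the same total. The shell prints counts visit by visit and never sums Yes over visits.
- That Protocol 4.5.1 names leg findings in general as a related risk. It names leg thrombus, as a serious adverse event.
- That sites did record improvements inconsistently. The SAP shows a mismatch between the CRF wording and its own instruction, which makes under-recording possible but does not demonstrate it.

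It is also fair to object to rebuilding baseline-referenced status at every visit by carrying results forward. If a return to Normal was not entered, the finding would stay Abnormal indefinitely. Most later examinations are symptom-directed, so status would also be assigned to systems that may not have been examined. That objection is accepted in the fix.

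**Conclusion.** The point holds. The protocol and SAP use different reference points for the same summary, Section 9 does not say so, and the SAP version pools improvement with deterioration and drops persisting findings. Section 9's closing sentence permits later disclosure but does not make the table interpretable.

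The consequence is modest. This is one descriptive, untested safety table; it does not affect the OS analysis, and clinically important findings have a second route through adverse event reporting. The conclusion assumes the table is programmed as the shell shows. The sequences above are illustrations, because the documents give no PE results. The change is worth making because it is cheap and because the table as drafted can mislead about which arm did worse.

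**What to change.** In SAP 7.7.6 and Table 14.3.10.2:

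1. Split Yes at each visit into subjects with at least one body system recorded as changed to Abnormal, and subjects with at least one recorded as changed to Normal. A subject may appear in both rows.
2. Add one row per subject, over all visits: any body system recorded Abnormal after baseline that was Normal at Pre-Study/Baseline. Listings 16.2.11.1 and 16.2.11.2 supply the data. In the illustration this row counts (a) and (b) but not (c).
3. Divide the by-visit rows by subjects examined at that visit.
4. Do not carry body-system status forward across visits as the main display. Footnote that the CRF wording asked only for Abnormal changes, so improvements may be under-recorded, and that most later examinations were symptom-directed.
5. Record in Section 9 whatever still differs from the protocol, including that the by-visit rows remain relative to the previous examination.

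The cost is a little programming and no new data. Worsening within a system that was already Abnormal will still have to be read from the text description, and the by-visit rows will not show how long a finding lasted.

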#### 8. MISSING DATA

Missing dates will be imputed only when the date is required to calculate the duration of an event for summary. As such, the only missing date that would need to be imputed is the date of final dose, required for calculation of duration of treatment. In such situations, the month and year would be recorded. For subjects who have completed dosing, the missing date of final dose will be imputed as the 15-th of the month; for subjects who are still receiving treatment, the missing date of final dose will be imputed as the date of the last completed visit.

Missing data from intermediate visits for AFP, WBC A3AR, viral load, and laboratory assessments when considered exploratory efficacy variables will be imputed using Last Observation Carried Forward (LOCF). Missing data for the latter laboratory variables will not be imputed when examined with laboratory assessments as safety variables. Due to the nature of the study, there is no imputation due to discontinuation.

The protocol specifies that certain assessments will not be repeated at Baseline (Cycle 1 Day 1) if assessed at the Pre-Study visit <= 3 days prior to Cycle 1 Day 1, resulting in missing values for Baseline; in such cases, the missing value at Baseline will be imputed by the value from the Pre-Study visit.

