9.0 EFFICACY AND SAFETY VARIABLES ASSESSED

9.1 Trial Visits

All subjects will be assessed by scheduled clinical, laboratory, and other diagnostic assessments throughout the trial. See the flow chart ([Table 1–1](#) and [Table 1–2](#)) for the timing of trial procedures and assessments to be performed at each clinic visit.

Pre-Study (i.e., Screening) assessments are to be performed within 28 days prior to first study drug dose, unless otherwise specified.

*The first day of study drug dosing will be considered Day 1 (**Baseline**) of the trial.*

Clinic Visits will take place within ± 2 working days of the scheduled time unless a waiver is approved by the Sponsor. Trial assessments will be performed prior to administration of the study drug dose for that day.

If significant changes from baseline are noted during the trial, additional unscheduled clinic visits may be performed in order to determine the relevance of findings and/or the duration of events.

End of Dosing assessments are to be performed within 2 working days after the last dose of study drug.

A **Follow-Up** visit is to be scheduled 28 ± 3 days after the **End of Dosing** visit to perform all final safety assessments and collect information on any adverse events.

The subjects who are still on blinded treatment when the Amendment 5 is approved will be switched to open label treatment at their next scheduled visit. During this visit, the Cycle 1 Day 1 for OL procedures will be performed ([Table 1-2](#)). In OL period, Clinic Visits will take place within ± 2 working days of the scheduled day unless a waiver is approved by the Sponsor. Trial assessments will be performed prior to administration of the study drug dose for that day.

*The first day of open label study drug dosing will be considered Day 1 (**OL**) of the trial.*

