#### 7.5 MEDICATION AND TREATMENT ANALYSIS

#### 7.5.1 COMPLIANCE AND EXPOSURE

Compliance will be calculated as the number of total capsules dispensed (over the duration of the study) minus the total number of capsules returned, and then that quantity is divided by twice the duration of treatment in days. The duration of treatment is date of final dose minus date of Baseline + 1. If the date of final dose is missing or if the subject is still receiving treatment, the date of final dose will be imputed as described in Section 8. Descriptive statistics for compliance and the duration of treatment will be provided for the Safety Population by treatment. The summary statistics pooled across treatments will also be computed for duration of treatment, to be used in efficacy evaluations as described in Sections 7.6.1-7.6.3.

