**Listing 16.2.7** 

#### Adverse Events

Site/ Subject	Treatment	System Organ Class / Preferred Term/ Verbatim Term	Start Date	Stop Date (1)	Duration (2)	Severity Grade (3)	Frequency (4)	Relation (5)	Action Taken (6)	Outcome (7)	Serious?
xxx/xxxx	XXXXX	xxxxxx /	DD/MM/YY	DD/MM/YY	Х	Х	Х	х	Х	Х	XX
xxx/xxxx	xxxxx	xxxxxx/ xxxxxxx xxxxxx /	DD/MM/YY	DD/MM/YY	V	x	v	v	v	v	XX
****	****	XXXXXX/ XXXXXXXX	DD/IVIIVI/ I I	DD/WIW/TT	*	^	*	*	X	X	**

Sorted by Start Date, then alphabetically by SOC and Preferred Term within subject.

Programming Note: Sort by Start Date, then alphabetically by SOC and Preferred Term within subject for AEs starting on the same date.

 O=AE ongoing

 Duration (days)= Stop Date - Start Date + 1; Duration = Date of Last Dose - Start Date + 1 if AE is ongoing

 Severity Grade: 1=Mild, 2=Moderate, 3=Severe or medically significant but not immediately life-threatening, 4=Life-threatening consequences, or 5=Death related to AE.

 Frequency: 1= Single episode 2= Intermittent 3= Continuous

 Relationship: 1= Definitely related 2= Probably related 3= Possibly related 4= Not related

 Action Taken: 0= None 1= Medication TX 2= Non-medication TX 3= Hospitalization 4= Study drug delayed, 5= Study drug discontinued

 Outcome: 1= Resolved 2= Resolved with sequelae 3= Unresolved 4= Death

Listing 16.2.8.1 Clinical Laboratory Evaluations: Hematology

Site/ Subject	Treatment	Visit	Day	Date	Laboratory Parameter (Units)	Value (1)	CFB
xx/xxxx	XXXXX	Pre-Study		MM/DD/YYYY	XXXXXXXXXXXXXXXXXXXXXXXXXXXXXXXXXXXXXX	XXX	
		-			XXXXXXXXXXXXXXXXXXXXXXXXXXXXXXXXXXXXXX	XXX	
					XXXXXXXXXXXXXXXXXXXXXXXXXXXXXXXXXXXXXX	XXX	
		Baseline		MM/DD/YYYY	XXXXXXXXXXXXXXXXXXXXXXXXXXXXXXXXXXXXXX	XXX	
					XXXXXXXXXXXXXXXXXXXXXXXXXXXXXXXXXXXXXX	XXX	
					XXXXXXXXXXXXXXXXXXXXXXXXXXXXXXXXXXXXXX	XXX	
		Cycle 1	8	MM/DD/YYYY	XXXXXXXXXXXXXXXXXXXXXXXXXXXXXXXXXXXXXX	XXX	XXX
					XXXXXXXXXXXXXXXXXXXXXXXXXXXXXXXXXXXXXX	XXX	XXX
					XXXXXXXXXXXXXXXXXXXXXXXXXXXXXXXXXXXXXX	XXX	XXX
		Cycle 1	15	MM/DD/YYYY	XXXXXXXXXXXXXXXXXXXXXXXXXXXXXXXXXXXXXX	XXX	XXX
					XXXXXXXXXXXXXXXXXXXXXXXXXXXXXXXXXXXXXX	XXX	XXX
					XXXXXXXXXXXXXXXXXXXXXXXXXXXXXXXXXXXXXX	XXX	XXX
		Cycle 2	1	MM/DD/YYYY	XXXXXXXXXXXXXXXXXXXXXXXXXXXXXXXXXXXXXX	XXX	XXX
					XXXXXXXXXXXXXXXXXXXXXXXXXXXXXXXXXXXXXX	XXX	XXX
					XXXXXXXXXXXXXXXXXXXXXXXXXXXXXXXXXXXXXX	XXX	XXX
		Cycle 2	15	MM/DD/YYYY	XXXXXXXXXXXXXXXXXXXXXXXXXXXXXXXXXXXXXX	XXX	XXX

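### For subjects who have completed dosing, an unbounded 15th-of-month imputation of the final-dose day can give impossible treatment durations and compliance values

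*SAP*

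**What the plan says.** SAP 8 names the date of final dose as the only date that needs imputing, because treatment duration depends on it. On what is known when the day is missing, it says: "In such situations, the month and year would be recorded". Two rules follow:

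- Dosing finished: "the missing date of final dose will be imputed as the 15-th of the month".
- Dosing ongoing: "for subjects who are still receiving treatment, the missing date of final dose will be imputed as the date of the last completed visit".

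SAP 7.5.1 uses the result twice. For duration: "The duration of treatment is date of final dose minus date of Baseline + 1". For compliance, capsules dispensed minus capsules returned are taken, and "that quantity is divided by twice the duration of treatment in days". Table 14.1.7 prints the mean, SD, median, minimum and maximum of both. The duration summary pooled over arms also sets the time at which the OS, TTP and PFS curves are read (SAP 7.6.1 to 7.6.3).

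A nearer date is normally on file. Protocol 9.1 says: "End of Dosing assessments are to be performed within 2 working days after the last dose of study drug". The schedules of events in both documents give the window as 2 days. Date of first dose and date of death are in Listing 16.2.5.1, and drug accountability by visit is in Listing 16.2.4.2.

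**The concern.** A mid-month convention is common, but it is normally limited by dates that are known. Here no limit is stated, either in SAP 8 or elsewhere. The rule can therefore contradict recorded facts: dosing after death, dosing that ends before a visit at which the subject was on drug, or dosing that ends before it began. The last case makes duration zero or negative, and compliance undefined or negative.

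The trial has some exposure to this. Treatment continues until drug-related intolerability, and documented progression does not stop it (protocol 9.2.12), so dosing can run close to death. Entry requires a life expectancy of only 6 weeks or more. One impossible value would become the printed minimum in Table 14.1.7 and would pull on the mean and SD.

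**Working it through.** The plan states no figure to reproduce here, so the check applies its formulas to calendar dates.

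**Inputs.** Imputed final dose = 15th of the recorded month (SAP 8). Duration = final dose - Baseline + 1, and compliance = 100 x capsules taken / (2 x duration) (SAP 7.5.1). The examples are mine and assume that every capsule was taken, two a day. The year is 2016.

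| First dose | True last dose | Imputed | True duration | Duration under the rule | Compliance under the rule |
|---|---|---|---|---|---|
| 20 March | 28 March | 15 March | 9 | 15 - 20 + 1 = -4 | 18 / (2 x -4) = -225% |
| 16 March | 26 March | 15 March | 11 | 15 - 16 + 1 = 0 | 22 / 0, undefined |
| 10 January | 4 March, death 6 March | 15 March | 55 | 66 | 110 / 132 = 83.3% |
| 10 January | 30 March | 15 March | 81 | 66 | 162 / 132 = 122.7% |

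- Rows 1 and 2: the final dose precedes the first dose.
- Row 3: dosing runs 9 days past death.
- Row 4: Cycle 3 Day 15 is 70 days after 10 January, which is 20 March. The imputed last dose falls 5 days before a scheduled visit at which the subject was still on drug.

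**Size of the error.** I replaced every possible last-dose date over two years by the 15th of its month, taking dates as uniform:

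- Imputed minus true date runs from -16 to +14 days. The mean absolute error is 7.6 days, and 84% of dates are off by more than 2 days.
- If death comes 0, 1 or 2 days after the last dose, the imputed date falls after death in 46%, 43% and 39% of cases.
- If the last on-drug visit was 0 to 13 days before the last dose (uniform), the imputed date precedes that visit in 29% of cases.
- Duration is zero or negative in 31% of cases when the true duration is 7 days, 8% at 14 days, 2% at 16 days, and never at 17 days or more.

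These percentages are conditional on a missing day in a subject who has finished dosing, and on the uniform assumptions. They are not estimates for this trial.

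**Comparison with the End-of-Dosing visit.** A visit held on time gives an error of 0 to 2 days, or up to 4 calendar days when 2 working days span a weekend.

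**The case against.** The strongest reply is that this is a corner case in descriptive data, and much of that stands. Non-positive durations need a true duration of 16 days or less, a start and stop after mid-month in the same month, and a missing day. The protocol cites a median survival of generally no more than 2 months after sorafenib failure (4.5.2), but also medians of 9.5 months in Child-Pugh B subjects and 7.2 months after sorafenib in the earlier CF102 study (4.2.2). Listing 16.2.4.1 prints final dose, Baseline, duration and compliance side by side, so a negative value would probably be noticed. An 11-day overstatement, as in row 3, would be less conspicuous. Review of listings is also no substitute for a bound in the rule.

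Three stronger readings are tempting, but the documents do not support them:

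- **That every missing day becomes the 15th.** Subjects still on treatment get the date of their last completed visit.
- **That the imputed date also distorts the durations of ongoing adverse events.** Listing 16.2.7 does use the last dose: "Duration = Date of Last Dose - Start Date + 1 if AE is ongoing". But SAP 8 limits imputation to durations needed for a summary and names only treatment duration. No planned table summarises AE duration, and the reporting conventions present dates as recorded. Nothing says that the imputed date enters there.
- **That the End-of-Dosing visit always dates the last dose to within 2 days.** Protocol 9.1 allows 2 working days, visits can run late, and a subject who dies on treatment may have none. Used without limits, the visit can also fall outside the recorded month: last dose 31 March, visit 2 April.

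**Conclusion.** The point holds in a limited form. As written, the rule for subjects who have completed dosing can produce each of the three impossible orderings, and through SAP 7.5.1 a zero or negative duration and an undefined or negative compliance. The error is at most 16 days per affected subject.

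The consequence is small. It touches the duration and compliance cells of Table 14.1.7. It also touches, slightly, the pooled median duration at which the survival curves are read, and a median moves little for a few errors of this size. A reader might infer that the primary result is at risk. It is not: the logrank tests of OS, TTP and PFS do not use the final-dose date. The documents do not say how many final-dose dates lack a day, and the number may be zero. This is a cheap correction worth making, and no conclusion of the trial turns on it.

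**What to change.** First count the final-dose dates with a missing day. Then replace the rule for subjects who have completed dosing in SAP 8 by the following:

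- Use the End-of-Dosing visit date where that visit took place, otherwise the 15th of the recorded month.
- In both cases, the date may not be earlier than the latest of Cycle 1 Day 1, the last visit at which the subject was on drug, and the first day of the recorded month.
- In both cases, the date may not be later than the earlier of death and the last day of the recorded month.

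On the examples above:

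- Row 1 with a visit on 30 March gives 30 - 20 + 1 = 11 days against a true 9. With no End-of-Dosing visit but an on-drug Day 8 visit on 27 March, it gives 8.
- Row 3 with no visit is capped at death on 6 March and gives 57 days against 55.
- Row 4 with a visit on 1 April is capped at 31 March and gives 82 days against 81.

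The cost is a short edit to SAP 8 and a minimum and maximum in the program, using dates already collected. There are two drawbacks. The visit anchor overstates duration by the few days between last dose and visit, and by more if the visit is late. The change would also come after unblinding, since SAP 7.6.8 and 9 already record post-unblinding decisions. It must be disclosed as such in SAP 9 or the clinical study report. The rule is mechanical and the same in both arms, so the risk of bias from changing it late is minimal.
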